4.4 Early Withdrawal of Subjects

4.4.1 When and How to Withdraw Subjects

If the patient is unable to comply with the study protocol or they wish to withdraw from the study their participation in the study will be terminated. If the interscalene nerve block catheter becomes occluded or is pulled out prematurely, patients will remain in the study as our primary analysis will be performed based on the intention to treat.

In order to account for 10% dropout, which includes patients terminated from the study, a total sample-size of N=129 (43 per group) is proposed. Follow-up will not be performed for patients terminated from the study due to voluntary purposes.

If the patient chooses not to participate he or she will be provided the current perioperative care plan in place by the surgeon and will include pain management regardless of participation.

4.4.2 Data Collection and Follow-up for Withdrawn Subjects

Patients who voluntarily withdraw from the study will have their data collected in the perioperative and follow-up periods up to the point of termination.

Study team will determine if an adverse event occurred (section 8.1 of IND protocol) and will assess the relationship to study protocol (including study medications). If causality is certain, probable/likely, or possible as per WHO-UMC causality assessment system³⁹, study team will make every attempt to follow up with patient until adverse event is resolved.

Our primary analysis will be performed based on the intention to treat. A subgroup analysis will also be performed on patients who received the allocated treatment as per the planned protocol and.

The primary outcome for this study involves assessing its analgesic efficacy compared to other standard methods of regional anesthesia acute pain management techniques for patients undergoing total shoulder arthroplasty. Survival data will not be assessed in this study; thus, we will plan to exclude data after a patient's termination/withdrawal date.

If the patient chooses not to participate he or she will be provided the current perioperative care plan in place by the surgeon and will include pain management regardless of participation.

5 Study Drugs

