By enrolling in this study there will be no additional risk in the operation or postoperative care as these are already established modalities of care, and all acceptable alternatives. Known risks for peripheral nerve blockade include the following: bleeding, infection, and nerve damage.

Since the benefits of local infiltration analgesia within a comprehensive multimodal analgesia clinical pathway have yet to be established for total shoulder arthroplasty, differences in the analgesia outcomes between these three intervention groups would provide for an evidence-based clinical pathway that will emerge as a result of this study.

2 Study Objectives

Primary Objective

We aim to test the hypothesis that patients undergoing total shoulder arthroplasty within a clinical pathway utilizing preemptive low-dose opioid and non-opioid medications for multimodal analgesia randomized to the continuous interscalene nerve block group will report a lower OBAS score on POD 1 (from 9 am to 12 pm) when compared to randomization to the single injection interscalene blockade and local infiltration analgesia groups.

Overall benefit of Analgesic Score (OBAS) is a recently validated tool measuring patient’s experience with their postoperative pain regimen.¹⁷ This simple 7 question (Q1 to Q7) scoring system entails a combination of pain intensity, adverse opioid events, and patient satisfaction. Per Lehmann et al, the total OBAS score is calculated via ‘sum items Q1 through Q6 and add [4 – score from Q7].’¹⁷ This score consists of a 29-point scale ranging from 0 (best) to 28 (worst); therefore, lower OBAS scores indicate more analgesic benefit. This will be administered to patients on POD 1 by the study team.

Secondary Objective

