4.3 Subject Recruitment, Enrollment and Screening

After approval by Mayo Clinic IRB, we will work closely with the department of orthopedics at Mayo Clinic Hospital, Methodist Campus to enroll patients into the study. Potential subjects will consist of patients who present for elective primary TSA meeting the above inclusion and exclusion criteria (section 4.1 and 4.2). Subjects will be approached by study staff for

recruitment in person and informed consent will be obtained. Subjects unable to give consent themselves will not be approached for participation. No remuneration will be provided. All efforts will be made to enroll participants regardless of ethnic heritage. No passive recruitment methods (newspapers, advertisements, or flyers) will be used.

Research study coordinators will meet eligible participants at either their preoperative orthopedic appointment or the morning of surgery provided they are not the first surgical case of the day. A sufficient amount of time will be given to the patient to answer any questions he or she may have and to allow the patient to make a well informed decision.

Of note, study staff/clinical research unit, which includes the research study coordinators, is composed of RN's and RRT's. Given that this is an institutional initiated study, the study staff is able to enroll patients meeting all inclusion/exclusion criteria into the study. In the event that there are any questions or concerns, the study coordinators will contact the PI/Co-PI's.

Discussion of study participation will be conducted in a private room in the presence of the patient's family if he/she so desires. Information will be provided to the patient without any time pressure. Interruptions to this discussion will be minimized by holding this discussion after most of the necessary (not study related) preoperative patient care processes are completed. The study recruiter will be different from the care team. Patients will be reassured that participation in the study does not change in any way their care beyond the random allocation to one of the three intervention arms and subsequent data collection.

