5.3 Method for Assigning Subjects to Treatment Groups

The treatment allocation will be performed using a randomization schedule which will be created by the Division of Biomedical Statistics and Informatics. This randomization schedule will be generated using a SAS program (SAS version 9.3, SAS Institute Inc, Cary NC) with randomization performed in blocks of size N=6 to ensure that after every sixth patient is enrolled there are an equal number of patients assigned to each of the 3 treatment conditions. Using this randomization schedule, an EXCEL spreadsheet application will be created which will include sequentially assigned subject-ID numbers and corresponding treatment assignments. When a patient is enrolled they will be assigned the next sequential subject-ID number and a member of the anesthesia clinical research unit, who will be different from the care team and are not involved in the medical management of the patient, will use the online system to retrieve the allocated treatment assignment for this subject-ID.

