5.5 Subject Compliance Monitoring

Patients receiving treatment will be enrolled in a prospective database. No other treatment is necessary, except the treatment assignment during their scheduled procedure.

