7.3 Subject Population(s) for Analysis

Our primary analysis will be performed based on the intention to treat. Therefore, any subject randomized into the study, regardless of whether they received study drug, will be included in the primary analysis. A subgroup analysis will also be performed on patients who received the allocated treatment as per the planned protocol, and patients undergoing reverse vs anatomic primary TSA.

8 Safety and Adverse Events

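### Read literally, 4.4.2 drops the POD 1 OBAS of operated, consenting patients terminated for non-compliance, whom 7.3 keeps in the primary analysis; separately, 7.1 counts failed blocks as attrition although 6.2 retains them

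*Combined protocol and SAP*

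**What the plan says.** **Who is terminated.** Section 4.4.1 names two kinds of patient in one sentence: "If the patient is unable to comply with the study protocol or they wish to withdraw from the study their participation" is ended. Inability to comply is not defined. The same section says that no follow-up is done for terminations that are voluntary; it does not say this of other terminations.

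**What happens to their data.** Section 4.4.2 notes that survival is not assessed and continues: "thus, we will plan to exclude data after a patient's termination/withdrawal date". The wording covers termination as well as withdrawal and makes no exception for OBAS.

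**Who is analysed.** Section 7.3 states that "any subject randomized into the study, regardless of whether they received study drug, will be included in the primary analysis".

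**What is already retained.** If a catheter is occluded or "pulled out prematurely, patients will remain in the study as our primary analysis will be performed based on the intention to treat" (4.4.1). Section 6.2 keeps patients with a failed block under intention to treat. Section 7.2 makes all enrolled subjects evaluable whatever treatment follows.

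**Timing.** Patients are approached at "either their preoperative orthopedic appointment or the morning of surgery" (4.3). Section 5.3 says: "When a patient is enrolled they will be assigned the next sequential subject-ID number", and the allocation is then retrieved. OBAS is taken once, in a bedside interview on POD 1 between 9 am and 12 pm (sections 2 and 6.4).

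**Attrition.** Section 7.1 goes from 39 to 43 per group for about 10% attrition and gives cancelled surgery and failed block as examples. Section 4.4.1 describes the same 10% as dropout that includes terminated patients.

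**The concern.** OBAS is a single measurement taken the day after surgery. A patient terminated between randomization and that interview therefore has no primary outcome if 4.4.2 is followed as written, yet 7.3 counts that patient in the primary analysis. The reason 4.4.2 gives, that survival is not studied, has no bearing on a score collected on POD 1.

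The trial is unblinded, and what counts as being unable to comply is left to judgement. If such a judgement leads to an outcome being discarded after allocation is known, the comparison is exposed to the kind of selection that an all-randomized analysis is meant to exclude.

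The second matter is one of bookkeeping. Section 7.1 treats failed blocks as lost, and 6.2 treats them as analysed. The same patients cannot be both, and the reader cannot tell what the 10% allowance is for.

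**Working it through.** **1. The plan's own figures.** Inputs from 7.1: difference 3, SD 3, two-sided alpha 0.017, 39 per group; for NRS, 0.75 SD. With a noncentral t, the noncentrality is (difference/SD) × √(n/2) on 2n − 2 degrees of freedom.

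- OBAS, n = 39: 1 × √19.5 = 4.416, power 97.4%. This agrees with the stated value of over 90%.
- NRS, n = 39: 0.75 × √19.5 = 3.312, power 80.6%. This agrees with the stated 80%. With a rank-test efficiency of 0.955 applied to n, it is 78.4%.
- Inflation: 43 × 0.90 = 38.7, about 39. The allowance is 4 of 43 per arm, or 9.3%.

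**2. Which patients 4.4.2 affects.** The window runs from randomization to the POD 1 interview.

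| Patient | OBAS under the current text | Avoidable loss? |
|---|---|---|
| Terminated after the interview | Kept | No loss |
| Withdraws consent before the interview | None | No |
| Surgery cancelled | None exists | No |
| Catheter problem, failed block, study drug not received | Kept (4.4.1, 6.2, 7.3) | No loss |
| Operated, consenting, terminated as unable to comply before the interview | Excluded by 4.4.2 | Yes |

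Only the last row is at issue.

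**3. Whether another section restores the score.** Section 7.2 confines last observation carried forward to success rates, and OBAS has no earlier value to carry. Other adjustment is made only if judged necessary. The planned comparison of prognostic factors in subjects with and without data can describe selection but cannot supply an excluded score.

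**4. Illustrative size (assumed rates; the plan gives none).** Suppose k of 43 are lost from one arm only and their OBAS is D units worse than that of the rest. The shift in the arm mean is (k/43) × D. The standard error of the difference is 3 × √(1/43 + 1/(43 − k)), about 0.65. The last column is the pairwise type I error of a test set at 1.7%.

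| k | D | Shift | Shift/SE | Type I error |
|---|---|---|---|---|
| 1 | 3 | 0.070 | 0.107 | 1.8% |
| 1 | 6 | 0.140 | 0.214 | 1.95% |
| 2 | 3 | 0.140 | 0.213 | 1.9% |
| 2 | 6 | 0.279 | 0.426 | 2.7% |

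The shifts are 2% to 9% of the 3-unit target.

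**5. Failed blocks retained.** If a fraction f of an arm loses a share L of the benefit, the mean effect is multiplied by (1 − f × L). Both f and L are assumed.

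- NRS, n = 43, f = 5%, L = 1: effect 0.75 × 0.95 = 0.7125; 0.7125 × √21.5 = 3.304; power 80.5% (rank 78.4%). This nearly equals the plan's own 80.6% (rank 78.4%) at 39 with no failures. With f = 10% and L = 0.5 the product f × L is the same, and so is the power.
- Simulating the mixture directly (n = 43, f = 5%, L = 1) gives 79.7% for the t-test and 76.9% for the Wilcoxon test. The match to 80% is therefore approximate.
- OBAS, f = 10%, L = 1: noncentrality 0.9 × √21.5 = 4.173 at n = 43 and 0.9 × √19.5 = 3.974 at n = 39. Power is 95.7% and 93.5% (rank 94.7% and 92.2%). The lowest simulated value, Wilcoxon at 39, is 90.7%.

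**The case against.** The strongest reply is that the affected group is almost empty. The foreseeable departures are all retained, and 5.5 asks very little of patients: "No other treatment is necessary, except the treatment assignment during their scheduled procedure". It is hard to name an event that would make an operated, consenting patient unable to comply before the next morning. Section 4.4.1 stops follow-up only for voluntary terminations, which suggests that others may still be followed. Section 4.4.2 is headed for withdrawn subjects, opens with voluntary withdrawal, and restates intention to treat. Its survival sentence may only be explaining why nothing like the vital-status check in 9.1 is needed.

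Most of this stands, and it limits the point to a small group. It does not remove the point. The exclusion in 4.4.2 is worded to cover termination as well as withdrawal, inability to comply is a separate ground for termination in 4.4.1, and an intention-to-treat statement cannot supply a score that another sentence excludes.

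On failed blocks, the reply is that attrition is loose wording, that 6.2 is clear about the analysis, and that the planned subgroup of patients treated as allocated would lose these patients. It is also true that the step from 39 to 43 offsets the dilution from 5% failed blocks with all benefit lost, provided nobody else is lost. A reader might infer from the conflict that the 80% NRS power is missed. The documents do not support that. A clear shortfall at 43 per group (75.5% by t-test) needs an assumed 10% of failed blocks with no benefit at all, whereas 6.2 allows re-blocking or pain medication. These two-sample figures also do not represent the repeated-measures analysis that 7.2 plans for serial NRS.

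**Conclusion.** The point holds in a narrow form. Sections 4.4.1 and 4.4.2 together discard the POD 1 OBAS of an operated, consenting patient terminated for non-compliance before the interview, and 7.3 requires that patient in the primary analysis. Nothing in 7.2 repairs this. The number affected is probably small, and the size and direction of any bias are unknown. The shift of 0.07 to 0.28 units and the type I error of 1.8% to 2.7% rest on assumed losses in one arm only and are illustrations, not predictions.

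A reader might infer that the intention-to-treat analysis fails for every terminated patient. It does not: loss after withdrawn consent is unavoidable, cancelled surgery yields no OBAS, and patients terminated after the interview keep theirs.

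The conflict between 7.1 and 6.2 on failed blocks is real, but it is one of description. N=129 and the OBAS power above 90% stand in every case computed. The 80% NRS power holds approximately at 43 per group with 5% failed blocks and all benefit lost, if there is no other attrition. The change is worth making because it corrects a stated rule for the primary outcome at almost no cost.

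**What to change.** - **4.4.2:** limit the exclusion to data after withdrawal of consent, and delete the survival rationale.
- **4.4.1:** separate protocol deviation from withdrawal of consent, and define inability to comply or remove it. After a deviation, still collect the POD 1 OBAS and analyse it in the allocated arm.
- **7.3:** keep the population as it is. Report by arm the number of patients without OBAS and the reason, with cancelled surgery shown separately.
- **7.1:** remove failed block from the attrition reasons, so that it agrees with 6.2.
- **Optional:** one sensitivity analysis for missing OBAS, for example shifting the missing values by 0 to 6 units per arm, beside the comparison already planned in 7.2.

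The cost is a few sentences and one reporting table. OBAS is a short bedside interview already in the schedule, and the sample size does not change.

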5.1 Description

Pre-mixed bupivacaine 0.5% with epinephrine 1:200,000 is packaged within a clear glass vial, containing 150 mg (30 mL) of bupivacaine. Solution is sterile, and clear and colorless. Bupivacaine is readily available and commonly stocked at our institution. Similarly, ropivacaine is a sterile, and clear and colorless solution that is readily available and commonly stocked at our institution.

All drug products mentioned in this study are FDA approved and commercially available. All products are administered per product prescribing information without further manipulation.

5.2 Treatment Regimen

As mentioned above in section 1.3, the LIA group will utilize weight based dosing of Ropivacaine as part of a "cocktail" solution (Table 1), and will receive a total volume of 120 mL injected in the periarticular structures by the surgeon. This is a one-time injection. This will occur after implantation of the final prostheses, but prior to closure of the fascia. All surgeons will complete the infiltration following a similar protocol, equally distributing the study medication around the glenoid and humerus, subscapularis, deltoid, posterior capsule and subcutaneous tissue. Medications and dosage of the LIA group is as follows:

Table 1: LIA Group

Drug	50-74.9kg	75-99.9 kg	100-125kg
Ropivacaine	200 mg	300 mg	400 mg
Epinephrine	100 mcg	200 mcg	300 mcg
Ketorolac	30 mg	30 mg	30 mg

*Normal Saline will be added to bring the total volume to 120 mL

SISB and CISB groups will utilize pre-mixed bupivacaine 0.5% with epinephrine 1:200,000 vial for the initial loading bolus. CISB group will have a continuous catheter attached to a pain pump infusing bupivacaine 0.2% when the patient arrives to the PACU.

Table 2 demonstrates the study medication for SISB and CISB groups.

Table 2: CISB and SISB Group – Bolus Injection

Nerve Blocked	Local Anesthetic	Concentration	Volume milliliters (mL)	- Adjuvants Added
Interscalene Brachial Plexus – CISB and SISB	Bupivacaine	0.5%	15 to 20 mL	1:200,000 Epinephrine

Please refer to section 6.2 for the SISB and CISB groups' technique and administration of local anesthetic.

5.3 Method for Assigning Subjects to Treatment Groups

The treatment allocation will be performed using a randomization schedule which will be created by the Division of Biomedical Statistics and Informatics. This randomization schedule will be generated using a SAS program (SAS version 9.3, SAS Institute Inc, Cary NC) with randomization performed in blocks of size N=6 to ensure that after every sixth patient is enrolled there are an equal number of patients assigned to each of the 3 treatment conditions. Using this randomization schedule, an EXCEL spreadsheet application will be created which will include sequentially assigned subject-ID numbers and corresponding treatment assignments. When a patient is enrolled they will be assigned the next sequential subject-ID number and a member of the anesthesia clinical research unit, who will be different from the care team and are not involved in the medical management of the patient, will use the online system to retrieve the allocated treatment assignment for this subject-ID.

5.4 Preparation and Administration of Study Drugs

Please refer to section 5.2 with regards to treatment regimen and administration of the “cocktail” solution for the LIA group.

Pharmacy prepares the weight based dose Ropivacaine, Epinephrine, Ketorolac 30 mg, in Normal Saline 0.9% (for a total volume of 120 mL) and provides this to the surgical staff. The Department of Pharmacy follows United States Pharmacopeia (USP) <797> preparation standards.⁴⁰ In general, the pharmacy uses environmental engineering controls for air quality of the preparation area, personal protective equipment during compounding, and performs preparation within laminar flow hoods. This “cocktail” solution will be dispensed to OR personnel during the surgical procedure.

The pre-made “cocktail” solution will be placed in a sterile basin located on the operating room table, within the vicinity of the surgeon and operating room technician, who are scrubbed into surgery. Sterility includes a sterile environment such as the operating room, in which a sterile field is created utilizing sterile surgical drapes. Operating room personnel handling the study

solution will be in sterile gloves and surgical gowns, hats and masks, and standing close to the surgical field.

In the SISB and CISB groups, one vial of pre-mixed bupivacaine 0.5% with epinephrine 1:200,000 will be obtained from the anesthesia stock room. Solution is sterile and will be poured in a sterile fashion into the sterile nerve block tray.

5.5 Subject Compliance Monitoring

Patients receiving treatment will be enrolled in a prospective database. No other treatment is necessary, except the treatment assignment during their scheduled procedure.

5.6 Prior and Concomitant Therapy

Patients may receive therapy for any conceivable condition, while enrolled in this trial, as long as they meet the inclusion criteria (section 4.1). Since this clinical trial is assessing analgesia efficacy between three different intervention arms, rescue analgesics will be available to all patients for uncontrolled pain as this is a standard practice at our institution.

5.7 Masking/Blinding of Study

This prospective randomized control trial will be unblinded. We acknowledge that this unblinded study design may be a limitation. We understand that there may be no way for us to prevent participants from being treated differently if the study is unblinded. They may have a different experience dependent upon the intervention biasing their observed outcome. However, we hope to discover the best overall clinical pathway for management of TSA for our patient population.

It would be very difficult to blind patients to the three intervention arms because each intervention arm involves a different nerve block technique (interscalene brachial plexus block⁴¹ vs local infiltration analgesia¹¹). The SISB and CISB groups involve placing a regional anesthesia peripheral nerve block, which is typically done in an awake patient prior to the surgical procedure. The LIA group will have their block performed by the surgeon, while the patient is under general anesthesia, towards the end of the surgical case just as the surgeon is about to close the fascia.

6 Study Procedures

